### CONFIDENTIAL

Q1W Cohort	Study Mair	ntenance Period			
Study Procedure	GSK417	Weekly (Q1W)	TDVª	Follow-Up (post-final dose administer ed	Notes
Week		1 and Thereafter	+4		
Day	-1	1 and Thereafter	+30d		
Safety Laboratory As	sessments				
Pregnancy Test		х	x	x	Urine pregnancy test will be conducted every 4 weeks for duration of study, on last day of treatment (if possible), at TDV, and at the Follow-Up visit.
CBC with differential	Х	Q1W	x		Sample collection times: Day –1 (single sample) and Day 1 at predose, EOI+4h and EOI+24h. At least every 6 hours for the first 48 hours following initiation of daily dosing period, then at least twice daily up to an including Day 5 dosing of each daily dosing period, and more frequently as clinically indicated.
Clinical Chemistry and TLS labs	х	Q1W	x		Sample collection times: Day –1 (single sample) and Day 1 at predose, EOI+6h, +12h, +18h and +24h; see Section 10.2 for complete list of required laboratory assessments.
C-Reactive Protein		Q1W	x		Sample collection times: predose, EOI+8h, and EOI+24h.
Thyroid function b		Day 1, then Q8W	X		The first assessment should be done at Week 1 and then Q8W.
Troponin I and T		Q2W	X		Sample will be collected predose and every 2 weeks.
BNP (or NTproNBNP)	X	Repeat as clinically indicated			Repeat test as outlined in management of cardiac events (Section 6.4.1.5)

### CONFIDENTIAL

					110000
Q1W Cohort	Study Ma	intenance Period			
Study Procedure	GSK417	TDVª	Follow-Up (post-final dose administer ed	Notes	
Week		1 and Thereafter	+4		
Day	-1	1 and Thereafter	+30d		
Urinalysis b		Q1W	х		If urinalysis is abnormal, a microscopy should be performed.
Coagulation b		Day 1, then Q3W			The first assessment should be done at Day 1 and then Q3W. Additional coagulation samples should be collected in the event of CRS (see Section 6.4.1.4)
Study Intervention		·			
Administer GSK3745417		Q1W			GSK3745417 must be administered with $\pm 1$ day of scheduled visit unless otherwise indicated. Each subsequent dose in a participant should be administered at least 5 days apart. See Section 4.1 duration of study intervention.
Non-Azole Antifungal	Х	Х	Х		Non-azole antifungals should be administered if indicated, per local standard, on Day -1 through Day 28 of each cycle.
Tumor Lysis Syndrome Prophylaxis	Х				All participants should receive tumor lysis syndrome (TLS) prophylaxis prior to date of GSK3745417 administration starting on Day -1 and continuing over 24 hours according to institutional guidelines (e.g., participants should receive IV fluids ± allopurinol and consider alkalization of urine and renal consult). Refer to Section 6.4.1.2 for prophylaxis and management of TLS.

### CONFIDENTIAL

					1166666
Q1W Cohort	Study Main	ntenance Period			
Study Procedure	GSK417	Weekly (Q1W)	TDVª	Follow-Up (post-final dose administer ed	Notes
Week		1 and Thereafter	+4		
Day	-1	1 and Thereafter	+30d		
Efficacy Assessment	ts				
Follow-up for survival				Q4W	Participants will be followed Q4W (±2 weeks) for survival and subsequent anti-cancer therapy. The survival follow-up visit will commence after discontinuation of study intervention.
BM Sample for Disease Assessment		Q6W during the 1⁵t three months, then Q12W			Both BM aspirate and core biopsy samples should be collected for Disease Assessment every 6 weeks during the first three months (2 time points) and then Q12W thereafter until disease progression or initiating another cancer treatment.
Pharmacokinetics (P	K), Pharmacodynamics and	d Genomics			
BM Biopsy		Q6W during the 1⁵t three months, then Q12W			On-treatment BM aspirate and core biopsies are both required during the maintenance phase until disease progression. Sample collection should be performed within EOI+48 hours but allowed window is +7 days after the scheduled visit. Alternative on-treatment biopsy timings may be explored, as discussed with GSK Medical Monitor. Unscheduled BM biopsies may be performed any time during the treatment period upon participant consent for this optional procedure.

#### CONFIDENTIAL

209809 Protocol

Q1W Cohort	Study Mai	ntenance Period			
Study Procedure	GSK417	Weekly (Q1W)	TDVª	Follow-Up (post-final dose administer ed	Notes
Week		1 and Thereafter	+4		
Day	-1	1 and Thereafter	+30d		
Progressive Disease BM biopsy			x		Although not required, a BM aspirate and core biopsy at the time of disease progression is highly encouraged.
Whole blood (flow cytometry)		Weeks 1, 2, 3, 4	х		Sample collection time points: Day 1 (Predose, EOI+4h, EOI+8h, EOI+12h, and EOI+24h), Day 8 (Predose, EOI+8h), Day 15 (Predose, EOI+8h), and Day 22 (Predose only). Collection of samples at disease progression is optional.
Serum (cytokines)		Weeks 1, 2, 3, 4, then Q3W	Х		Sample collection time points: Day 1 (Predose, EOI+4h, EOI+8h, EOI+12h, and EOI+24h), Day 8 (Predose, EOI+8h), Day 15 (Predose, EOI+8h), and Day 22 (Predose only). After Day 22, samples will be collected Q3W (predose, EOI+8hr) until disease progression. Collection of serum samples at disease progression is optional.
GSK3745417 plasma PK		Weeks 1, 2, 3, 4, then Q3W			PK sample collection times: Week 3 at predose, EOI +5m, +15m, +30m, +45m, +1h, +2h, +4h, +6h, +8h, +12h, +24h; All other weeks at predose, EOI+1h, EOI +4h, and EOI +8h.

Abbreviations: AE= adverse event; AESI=adverse events of special interest; CBC=Complete blood count; d=day; ECG=electrocardiogram; ECHO=echocardiography; ECOG PS=Eastern Cooperative Oncology Group Performance Score; eGFR= Estimated glomerular filtration rate; EOI=end of injection; h=hour; ICF=informed consent form; m=minQ1W=Every 1 week; Q3W=Every 3 weeks; Q6W=Every 6 weeks; Q9W=Every 9 weeks; Q12W=Every 12 weeks; SAE=serious adverse event; W=week; TLS = Tumor Lysis Syndrome; TDV=treatment discontinuation visit.

#### CONFIDENTIAL

209809 Protocol

Timepoint Definitions for assessments:

X = Ánytime during visit (sampling date/time should be recorded) Predose = within 60 minutes before the start of the GSK3745417 injection EOI+5m = at 5 minutes ±2 minutes from the end of the GSK3745417 injection EOI+15m = at 15 minutes ±5 minutes from the end of the GSK3745417 injection EOI+30m = at 30 minutes ±5 minutes from the end of the GSK3745417 injection EOI+45m = at 45 minutes ±5 minutes from the end of the GSK3745417 injection EOI+45m = at 45 minutes ±5 minutes from the end of the GSK3745417 injection EOI+1h = at 1 hour ±15 minutes from the end of the GSK3745417 injection EOI+2h = at 2 hours ±30 minutes from the end of the GSK3745417 injection EOI+4h = at 4 hours ±30 minutes from the end of the GSK3745417 injection EOI+6h = at 6 hours ±30 minutes from the end of the GSK3745417 injection EOI+8h = at 8 hours ±1 hours from the end of the GSK3745417 injection EOI+2h = at 12 hours ±1 hours from the end of the GSK3745417 injection EOI+8h = at 18 hours ±1 hours from the end of the GSK3745417 injection EOI+12h = at 12 hours ±1 hours from the end of the GSK3745417 injection EOI+12h = at 12 hours ±1 hours from the end of the GSK3745417 injection EOI+2h = at 24 hours ±2 hours from the end of the GSK3745417 injection EOI+2h = at 24 hours ±2 hours from the end of the GSK3745417 injection

- a. The assessments required at the study treatment discontinuation visit must be completed within 30 days from the date study treatment was discontinued and must occur prior to the start of subsequent anti-cancer therapy; the window for this visit is +10 days.
- b. Procedures scheduled on study treatment administration days can be performed within 3 days prior to dosing day, unless otherwise specified.

# 1.3.5. Part 2 – GSK3745417 Maintenance Every 3 Weeks

### Table 4 Schedule of Activities (GSK3745417 Maintenance Every 3 Weeks- Part 2 only)

Q3W Cohort	Stu	dy Maintenance Period			
Study Procedure	G: V	SK417 Every 3 Veeks (Q3W)	TDV⁵	Follow-Up (post- final dose administered	Notes
Week		1 and Thereafter a	+4	Q4W	
Day	-1	1 and Thereafter	+30d		
Safety Assessments					
In-House Monitoring	х	Q3W			Participants should be monitored in a medically qualified unit/clinic/hospital starting on Day -1 and 24 hours following the administration of GSK3745417 on Day 1. This requirement may be eliminated as safety data emerge.
Physical Exam		Q3W	х		Brief or targeted physical exams will be performed on Day 1 at predose (within 1h prior to dosing), and as clinically indicated. Refer to Section 8.2.1 for physical examination details.
ECOG PS		Q3W	Х		
Vital Signs	х	Q3W	х		Vital signs should be collected at least 6 times on Day -1 within 24 hours prior to dosing and on Day 1 at predose (within 1 hour prior to dosing) and at EOI+30m, +1h, +2h, +4h, +6h, +8h, +12h and +24h.
Weight		Q3W	Х		
Echocardiogram		Week 1, then Q9W	x		If available, a 3D ECHO is preferred, otherwise a 2D ECHO may be performed. Where the quality of the ECHO examination is sub-optimal, MUGA scans may be used. The modality used at baseline should be repeated throughout the study to ensure comparison to baseline. At TDV, ECHO/MUGA does not need to be performed if an on-study ECHO has been conducted within the 4 weeks prior to visit.

### CONFIDENTIAL

Q3W Cohort	Stu	dy Maintenance Period			
Study Procedure	GSK417 Every 3 Weeks (Q3W)		TDV⁵	Follow-Up (post- final dose administered	Notes
Week		1 and Thereafterª	+4	Q4W	
Day	-1	1 and Thereafter	+30d		
Concomitant Medication Review		Continuous: Asse	ss at ea	ch visit from first dose	of study intervention
Follow-Up Phone Call		Х			Participants should be contacted by phone 24-72 hours following discharge from clinic to assess for any AEs or cytokine related events
Safety Laboratory As	sessm	ents			
Pregnancy Test		Х	Х	Х	Urine pregnancy test will be conducted every 3 weeks for duration of study, on last day of treatment (if possible), at TDV, and at the Follow-Up visit.
CBC with differential	х	Q3W	х		Sample collection times: Day –1 (single-sample) and Day 1 at predose, EOI+4h and EOI+24h. At least every 6 hours for the first 48 hours following initiation of daily dosing period, then at least twice daily up to an including Day 5 dosing of each daily dosing period, and more frequently as clinically indicated.
Clinical Chemistry and TLS labs	х	Q3W	x		Sample collection times: Day –1 (single-sample) and Day 1 at predose, EOI+6h, +12h, +18h and +24h; see Section 10.2 for complete list of required laboratory assessments.
C-Reactive Protein		Q3W	Х		Sample collection times: Predose, EOI+8h, and EOI+24h.
Thyroid function b		Day 1, then Q6W	Х		The first assessment should be done at Week 1 and then Q6W.
Troponin I and T		Q3W	Х		Sample will be collected predose and every 3 weeks.
BNP (or NTproNBNP)	х	Repeat as clinically indicated			Repeat test as outlined in management of cardiac events (Section 6.4.1.5)
Urinalysis b		Q3W	Х		If urinalysis is abnormal, a microscopy should be performed.
Coagulation b		Day 1, then Q3W			The first assessment should be done at Day 1 and then Q3W.

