### CONFIDENTIAL

Q3W Cohort	Q3W CohortStudy Maintenance PeriodStudy ProcedureGSK417 Every 3 Weeks (Q3W)				
Study Procedure			TDV⁵	Follow-Up (post- final dose administered	Notes
Week		1 and Thereafter a	+4	Q4W	
Day	-1	1 and Thereafter	+30d		
Study Intervention					
Administer GSK3745417		Q3W			GSK3745417 must be administered with $\pm 3$ day of scheduled visit unless otherwise indicated. Each subsequent dose in a participant should be administered at least 5 days apart. See Section 4.1 duration of study intervention.
Non-Azole Antifungal	х	Х	Х		Non-azole antifungals should be administered if indicated, per local standard, on Day -1 through Day 28 of each cycle.
Tumor Lysis Syndrome Prophylaxis	x				All participants should receive tumor lysis syndrome (TLS) prophylaxis prior to date of GSK3745417 administration starting on Day -1 and continuing over 24 hours according to institutional guidelines (e.g., participants should receive IV fluids ± allopurinol and consider alkalization of urine and renal consult). Refer to Section 6.4.1.2 for prophylaxis and management of TLS.
Efficacy Assessment	s				
Follow-up for survival				Q4W	Participants will be followed Q4W ( $\pm 2$ weeks) for survival and subsequent anti-cancer therapy. The survival follow-up visit will commence after discontinuation of study intervention.
BM Sample for Disease Assessment		Q6W during the 1 st three months, then Q12W			Both BM aspirate and core biopsy samples should be collected for Disease Assessment every 6 weeks during the first three months (2 time points) and then Q12W thereafter until disease progression or initiating another cancer treatment.
Pharmacokinetics (Pl	K), Pha	rmacodynamics a	nd Gen	omics	·
BM Biopsy		Q6W during the 1 st three months, then Q12W			On-treatment BM aspirate and core biopsies are both required every 6 weeks during the first three months (2 time points) and then Q12W thereafter until disease progression. Sample collection during the maintenance phase should be performed within EQI+48 hours but allowed window is +7 days after the scheduled visit.

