#### CONFIDENTIAL

209809 Protocol

Q3W Cohort	Stu	dy Maintenance Period			
Study Procedure	G: N	SK417 Every 3 Veeks (Q3W)	TDV⁵	Follow-Up (post- final dose administered	Notes
Week		1 and Thereafterª	+4	Q4W	
Day	-1	1 and Thereafter	+30d		
					Alternative on-treatment biopsy timings may be explored, as discussed with GSK Medical Monitor. Unscheduled BM biopsies may be performed any time during the treatment period upon participant consent for this optional procedure.
Progressive Disease BM biopsy			Х		Although not required, a BM aspirate and/or biopsy at the time of disease progression is highly encouraged.
Whole blood (flow cytometry)		Weeks 1, 2, 3, 4	х		Sample collection time points: Day 1 (Predose, EOI+4h, EOI+8h, EOI+12h, and EOI+24h), Day 8 (any time), Day 15 (any time), and Day 22 (Predose only). Collection of samples at disease progression is optional.
Serum (cytokines)		Weeks 1, 2, 3, 4, then Q3W	х		Sample collection time points: Day 1 (Predose, EOI+4h, EOI+8h, EOI+12h, and EOI+24h), Day 8 (any time), Day 15 (any time), and Day 22 (Predose only). After Day 22, samples will be collected Q3W (predose, EOI+8hr) until disease progression. Collection of serum samples at disease progression is optional.
GSK3745417 plasma PK		Weeks 1, 4, 7, 10, then Q3W			PK sample collection times: Week 7 at predose, EOI +5m, +15m, +30m, +45m, +1h, +2h, +4h, +6h, +8h, +12, and +24; All other weeks at predose, EOI+1h, EOI +4h, and EOI +8h.

Abbreviations: AE= adverse event; AESI=adverse events of special interest; CBC=Complete blood count; d=day; ECG=electrocardiogram; ECHO=echocardiography; ECOG PS=Eastern Cooperative Oncology Group Performance Score; eGFR= Estimated glomerular filtration rate; EOI=end of injection; h=hour; ICF=informed consent form; m=min; Q1W=Every 1 week; Q3W=Every 3 weeks; Q6W=Every 6 weeks; Q9W=Every 9 weeks; Q12W=Every 12 weeks; SAE=serious adverse event; W=week; TLS = Tumor Lysis Syndrome; TDV=treatment discontinuation visit.

Timepoint Definitions for assessments:

X = Anytime during visit (sampling date/time should be recorded)

Predose = within 60 minutes before the start of the GSK3745417 injection

EOI+5m = at 5 minutes  $\pm 2$  minutes from the end of the GSK3745417 injection

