Part 2: Efficacy will be evaluated after an induction phase in approximately 50 participants, 25 AML participants and 25 HR-MDS participants. The induction phase consists of a treatment regimen at the dose/doses determined to be safe in Part 1 (RP2D). The number of cycles, number of doses investigated in the induction phase, and/or dosing schedule of 5/2/5 q28d treatment will be determined and may be modified based on a review of safety and PK data generated from Part 1. After the induction phase, patients will continue to either a weekly (Q1W), every 3 weeks (Q3W), or less frequent dosing schedule for maintenance treatment, if a CR or PR is observed (See Response Criteria for Participants with AML Appendix 9; See IWG Criteria for Response for Participants with MDS Appendix 8). Participants with stable disease or PR after 3 induction cycles might receive additional cycles if the assessment by the investigator determined a benefit and GSK Medical Monitor agrees. Up to three dose levels for maintenance treatment will be evaluated in the maintenance dose escalation. The DLT period for the maintenance dose escalation portion of Part 2 will be 28 days starting at Day 1 of each cycle. Dose escalation for the maintenance schedule will start at the highest dose cleared for safety in Part 1. Part 2 will evaluate the efficacy of the induction regimen separately for AML and HR-MDS as well as the tolerability and duration of response of the Q1W or Q3W maintenance schedules to determine the best dose and schedule for further studies.

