# 4.1.1. Dose Limiting Toxicities (DLT)

All toxicities will be graded using National Cancer Institute – Common Toxicity Criteria for AEs (NCI-CTCAE), version 5.0.

An AE is considered to be a DLT if it is considered by the investigator to be clinically relevant and attributed (definitely, probably, or possibly) to the study intervention and meets at least 1 of the criteria listed in the table below. If an AE is considered related to the underlying disease it is not a DLT. The DLT period is 28 -days starting at Day 1 of each cycle. Participants unable to receive at least 70% of scheduled doses within the DLT

period for reasons other than toxicity (e.g., acute illness, disease progression) will not be considered evaluable.

Toxicity	DLT Definition			
Cytokine Release Syndrome (CRS)	Grade 3 or 4 (See Section 10.4)			
TLS	Grade 3 or Grade 4 TLS (Cairo Bishop criteria, Appendix 11) that cannot be managed/ is not resolved within 72 hours			
Liver Toxicity	ALT $\geq$ 3x upper limit of normal (ULN), plus bilirubin $\geq$ 2x ULN (>35% direct) or plus international normalized ratio (INR)>1.5 (Possible Hy's law)			
Other	
 
Grade ≥3 non-hematologic toxicity of any duration with the following exceptions:
 
Transient (≤ 72 hours) abnormal laboratory value without associated clinically significant signs or symptoms
 
Individual parameters of CRS which collectively constitute <grade 3="" crs<="" li=""> 
Nausea, vomiting, or diarrhea that improves with supportive care within 72 hours
 
Alopecia of any grade
 
Grade 3 fatigue with duration <7 days
 
Grade 3 headache that resolves with supportive treatment to ≤Grade 2 within 24 hours
 
G3 acute renal injury considered related to TLS which improves or resolves with appropriate fluids and management of TLS
 
Grade ≥3 immune-related toxicity that does not resolve to Grade ≤1 or baseline within 8 days despite adequate immune suppressive therapy. Any other event which in the judgment of the investigator and GSK Medical Monitor is considered to be a DLT.
 </grade>

			

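### The Q3W maintenance schedule (Protocol Table 4) has no chemistry for about 19 days between doses, so some asymptomatic laboratory DLTs in the 28-day escalation window may be missed

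*Protocol*

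**What the plan says.** Table 4 (Protocol Section 1.3.5, Part 2 only) takes chemistry and TLS laboratory tests on Day -1 and from predose to 24 hours after the injection, once per three-weekly dose: "Day 1 at predose, EOI+6h, +12h, +18h and +24h; see Section 10.2 for complete list of required laboratory assessments". Table 3 (Section 1.3.3, weekly maintenance) has the same per-dose pattern, repeated each week.

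Section 4.1 fixes the window in which toxicity is counted: "The DLT period for the maintenance dose escalation portion of Part 2 will be 28 days starting at Day 1 of each cycle". Section 3 makes DLT frequency during maintenance a Part 2 primary endpoint, and Section 9.2 feeds the counts into the mTPI table (Figure 8) with 3 to 6 participants per dose level.

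Table 7 (Section 4.1.1) contains DLT criteria that only blood chemistry can show. One is ALT at 3 x ULN or more together with raised bilirubin or INR. Another is any non-hematologic toxicity of Grade 3 or above, with an exception for a transient (72 hours or less) "abnormal laboratory value without associated clinically significant signs or symptoms".

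Table 4 also has blood drawn between doses, but only for flow cytometry and cytokines. After Day 1 those draws are listed as "Day 8 (any time), Day 15 (any time), and Day 22 (Predose only".

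**The concern.** The DLT count is meant to cover 28 days. On Q3W the chemistry needed for several DLT criteria is scheduled at the start of that window and again around the second dose, with a long blank between. An asymptomatic liver or electrolyte abnormality gives the participant no reason to report and the site no reason to test, so it could come and go unrecorded.

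Two things are at stake. First, mTPI decisions rest on very few participants: in Figure 8, 1 DLT in 3 means stay and 0 in 3 means escalate, so one uncounted event changes the recommendation. Second, Section 4.1 says that Part 2 will look at the tolerability of Q1W or Q3W maintenance to settle the dose and schedule for later studies. A laboratory DLT is more likely to be observed under weekly sampling than under three-weekly sampling, whatever the drug does.

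**Working it through.** **Inputs.** Chemistry times come from Tables 3 and 4, the 28-day window from Section 4.1, the ±3-day Q3W dosing window from Table 4 and Section 6.1, and the mTPI table from Figure 8. Day -1 is taken as the day before each dose.

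**1. The plan's decision table.** The mTPI rule was run with a Beta(1,1) prior, target 0.30, epsilon1 0.05 and dose exclusion when P(p > 0.30) > 0.95. Epsilon2 = 0.05 is assumed, because it cannot be read in the extracted figure. All 107 cells in rows 0 to 8 of Figure 8 are reproduced.

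**2. Calendar count within Days 1-28.** Each dose on day d gives chemistry on days d-1, d and d+1.

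| Schedule | Chemistry days | Days with / without | Longest interval |
|---|---|---|---|
| Q3W (doses Day 1, 22) | 1, 2, 21, 22, 23 | 5 / 23 | 21 - 2 = 19 days |
| Q1W (doses Day 1, 8, 15, 22, 29) | 1, 2, 7-9, 14-16, 21-23, 28 | 12 / 16 | 7 - 2 = 5 days |
| Q3W plus Days 8 and 15 | 1, 2, 8, 15, 21, 22, 23 | 7 / 21 | 15 - 8 = 7 days |

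With the second Q3W dose on Day 19 or Day 25, the interval is 18 - 2 = 16 or 24 - 2 = 22 days. The blank itself is Days 3 to 20, which is 18 days. Days 24 to 28 are a further 5, and 18 + 5 = 23 of 28 (82%).

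**3. Chance that an abnormality meets no scheduled sample.** Assume onset uniform over the 28 days, a duration of L days, and only samples within the DLT period counting. On Q3W, onset in the main interval is missed for 19 - L days (L ≤ 19), and all onset after Day 23 is missed (6 of 28 days on this scale). The missed share is (19 - L + 6)/28.

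| L | Q3W | Q1W | Q3W plus Days 8, 15 |
|---|---|---|---|
| 5 days | 20/28 = 71% | 4% | 36% |
| 7 days | 18/28 = 64% | 4% | 21% |
| 14 days | 11/28 = 39% | 4% | 21% |

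The 21% in the last column is the uncovered end of the window, 6/28.

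**4. Effect on escalation, for illustration.** The documents do not say what share of DLTs would be asymptomatic laboratory events, so the missed share m is an assumption. With true DLT rate p, the observed rate is q = p(1 - m). P(0 of 3) = (1 - q)³. P(at most 1 of 6) is binomial. Both results are escalate in Figure 8. For p = 0.40:

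| m | P(0 of 3) | P(at most 1 of 6) |
|---|---|---|
| 0% | 0.22 | 0.23 |
| 10% | 0.26 | 0.30 |
| 25% | 0.34 | 0.42 |
| 50% | 0.51 | 0.66 |

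**5. The 48-hour rule.** Section 6.4.1.2 asks for 6-hourly chemistry over 48 hours in the first dosing cycle and in cycles with a dose increase. Table 4 does not show this. If it applied after both Q3W doses, Days 3 and 24 would be added. The longest interval would be 21 - 3 = 18 days, with 21 of 28 days still without chemistry.

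**The case against.** A reader might infer that laboratory DLTs cannot be detected during most of the window. The documents do not support that. The Day 21-23 samples lie inside the DLT period and catch anything that persists. Asymptomatic values lasting 72 hours or less are not DLTs, and a DLT must also be judged clinically relevant and attributed to treatment. Adverse events are reviewed at each visit, a phone call follows discharge, Section 8 allows unscheduled safety samples, and Section 1.3 lets assessment timing change on emerging data.

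Nor can one say that the 72-hour exception is unworkable. Section 8.2.6 already requires clinically significant abnormal results to be repeated until they settle.

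The contrast with weekly maintenance is also partial. Coagulation is on Day 1 and then every three weeks in both tables, so the INR part of the liver criterion is scheduled alike.

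Finally, a bias of the schedule choice toward Q3W is only possible. Section 9.2 says that data from the solid tumor study will determine the maintenance schedule. No formal comparison of DLT rates is planned, and under Section 4.1.2 the committee weighs all safety and PK/PD data as well as the mTPI recommendation.

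All of this narrows the point, but a gap remains. The repeat rule needs a first abnormal value, the phone call includes no test, and unscheduled sampling depends on suspicion that a silent abnormality does not raise. The 48-hour rule shortens the interval by one day at most.

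**Conclusion.** The point holds in a limited form. Table 4 leaves about 19 days (16 to 22 with the dosing window) without scheduled chemistry inside a 28-day DLT period, where weekly maintenance leaves at most 5. What may be missed is an asymptomatic chemistry DLT that arises and resolves between Day 2 and about Day 21, or one that starts after Day 23. Escalation on Q3W could therefore be too permissive, and laboratory DLT rates on the two schedules would not be measured on equal terms.

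It is tempting to report the gap as 19/28, or 68% of days unsampled. That treats an interval as a day count. The counts are 18 unsampled days in the gap and 23 of 28 overall.

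The calendar figures follow directly from the tables. The missed-share percentages rest on uniform onset, and the escalation probabilities on assumed missed shares. SAP Section 4.8 states that no participants will be recruited to Part 2, and Part 1 maintenance uses the weekly table. No reported result is affected; the point matters for the protocol as designed and for any reuse of Table 4.

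**What to change.** In Table 4, add the clinical chemistry panel to the Day 8 and Day 15 blood draws already planned for flow cytometry and cytokines, at least during the 28-day DLT period of maintenance dose-escalation participants. The nominal longest interval falls from 19 to 7 days (24 - 15 = 9 if the second dose is given on Day 25). Days 24-28 remain without chemistry, and the protocol should say so. Table 4 and the 48-hour chemistry rule in Section 6.4.1.2 must also be reconciled, stating whether that rule applies to maintenance doses.

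The cost is two local laboratory panels per participant in the DLT period and a table edit, with no new visit. The added blood volume is small but should be checked against the limit of 275 mL per 4 weeks in Section 8.
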